### **US primary endpoint**

- An additional method is used to calculate the proportion of positive pruritus assessments up to the last report day before or on Day 168. In other words, the denominator to calculate the proportion will be (the last report day x 2). All missing data before or on the last report day will be considered as negative assessments. This estimated proportion of positive pruritus assessments at the patient level over the 24-week treatment period based on the Albireo ObsRO instrument will be analyzed using the same approach as for the primary analysis.
- To address the concern that results from subjects with a baseline AM or baseline PM average score less than 2 may be difficult to interpret, additional supportive analysis will exclude patients from the primary endpoint analysis who have a baseline AM or baseline PM average score that rounded to 0 or 1.
- A supportive analysis of pruritus assessments as a continuous endpoint will be conducted. The analysis will be performed by considering the impact of intermittently missing data as well as intercurrent events.

The monthly (28-day) average in change from baseline for AM and PM, respectively will be calculated. There is a total of 6 monthly averages for AM assessments and 6 monthly averages for PM assessments over the 24-week treatment period. A mixed-effect model for repeated measures (MMRM) will be used to compare treatment effects at the last 28 days for AM and PM, respectively. Since missing not at random (MNAR) may occur, missing monthly average will be imputed with data from control arm completers using multiple imputation (MI). If there are subjects in the active arms who discontinued the study due to, e.g., relocation, their missing values may be imputed using active arm completers. To simplify the MI procedure, the description below only pertains to imputation using placebo completers. The MMRM model will include baseline score, treatment group, time (in month), treatment-by-baseline interaction, treatment-by-time interaction and stratification factors (i.e., PFIC type and age category). Unstructured covariance matrix will be used.

The following procedures in MI will be followed:

1. Intermediate missing values are imputed by the Markov Chain Monte Carlo (MCMC) imputation model, so only monotone missing values exist after imputation. 200 imputed data

sets will be created.

2. Subjects are classified to 3 subgroups: a. Completers in the control arm without a missing average at the last 4 weeks. b. Subjects with a missing average at the last 4 weeks in any arm, and c. Completers in the active arm without a missing average in the last 4 weeks. Subjects in subgroup ‘a’ will be used to impute missing values for subjects in subgroup ‘b.’
  3. The monotone missing values are imputed chronologically using SAS Proc MI. This is done by each imputed data set from step 1.
  4. After the imputation, all subjects in the 3 subgroups are pooled and the data are sorted by the imputation ID from step 1.
  5. MMRM is used to compare treatment effect in the last 4 weeks. This is done by the imputation IDs from step 1.
  6. Proc MIAnalyze is used to summarize and conclude the results from step 5.
- If the comparison result from the analysis of MMRM with multiple imputation is significant, a tipping point analysis will be performed by reducing the imputed scores in placebo patients by 0.1 each time until the result is non-significant. In addition, the imputed scores in active patients will be increased by 0.1 each time till the result is non-significant.
  - The MMRM with multiple imputation will be conducted for monthly average of change from baseline in AM and PM scores, and for monthly average of change from baseline in daily worst score.

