## 3 STUDY DESIGN

### 3.1 General study design

This is a double-blind, randomized, placebo-controlled, Phase 3 study to investigate the efficacy and safety of 40 µg/kg/day and 120 µg/kg/day of odevixibat compared to placebo in children with PFIC Type 1 and 2.

The study includes a 35- to 56-day Screening Period followed by a 24-week Treatment Period and a 4-week Follow-Up Period. After completion of the Screening Period, eligible patients (20 per treatment group) will be randomized on Day 0 (Visit 3) in a 1:1:1 fashion to receive 40 µg/kg/day or 120 µg/kg/day of odevixibat, or a matching placebo. Study data will be periodically reviewed by an unblinded Data Safety and Monitoring Board (DSMB).

A total of approximately 60 patients with a clinical diagnosis of PFIC Type 1 or 2 that have been genetically confirmed will be randomized. The randomization will be done in blocks and stratified according to PFIC type (Type 1 and 2) and age category (6 months to 5 years, 6 to 12 years, and 13 to ≤18 years) to ensure approximate balance between dose schemes (1:1:1).

The study will target 15% of enrolled patients to be PFIC-1 patients. If enrollment of all PFIC-2 patients is completed and the 15% enrollment of PFIC-1 patients has not yet been achieved, then enrollment of PFIC-2 patients will continue to reach the total study target enrollment. An attempt will be made to randomize a minimum of 10 patients from each age category (6 months to 5 years, 6 to 12 years, and 13 to ≤18 years). A maximum of 5 patients that were treated in Study [A4250-003](#) will be allowed to participate in this study.

Patients who complete the Treatment Period and Visit 9 (Day 168, Week 24) in this study will be invited to participate in a 72-week open-label extension study ([A4250-008](#), EudraCT Number 2017-002325-38, subject to a separate study approval) in which all patients will receive odevixibat 120 µg/kg/day. Prior to [protocol amendment 6](#), patients who had completed at least 12 weeks of the Treatment Period and had either no improvement or intolerable symptoms were eligible to complete the End of Treatment (EOT) Visit and were offered the opportunity to enter Study [A4250-008](#).

There will be up to 10 clinic visits during the study and one scheduled telephone contact, as follows:

- Visit 1: Screening Period start. Patient is considered enrolled after signing the informed consent form (ICF) (Days -56 to -35)
- Visit 2: Screening Visit 2 (Days -28 to -7)

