## 5 SAMPLE SIZE AND POWER

For the EU and RoW, the primary analysis will be related to the serum bile acid responder endpoint. For the US, the primary analysis will be related to the pruritus endpoint. The CMH test stratified by randomization strata will be used to test the serum bile acid responder endpoint. The individual null hypothesis is that the odds ratio of the response in an active arm vs. placebo is 1. The alternative hypothesis is that the odds ratio is greater than 1. An ANCOVA will be used for treatment comparisons for the proportion of positive pruritus assessments at subject level. The individual null hypothesis is that the average proportion of positive assessments is the same between the active and placebo arms. The alternative hypothesis is that the average proportion is larger in the active arm.

Since each active arm will be compared with the placebo, there will be two individual null hypotheses for each endpoint. In each endpoint, a pooled analysis for the closed testing procedure will be applied to control the 1-sided overall type I error rate for the two odevixibat treatment comparisons vs. placebo at the 0.025 level [6,7,8]. The significance of an active arm will be claimed if both 1-sided p-values in the pooled analysis and individual treatment comparison are less than or equal to 0.025.

The study will enroll 60 to 70 patients in order to obtain at least 20 evaluable patients in each arm. For each primary endpoint, simulations with 5,000 iterations using 20 patients per arm were conducted to estimate the power after multiplicity adjustment, resulting in a standard error (SE) of <0.7% for each estimated power.

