Based on the Phase 2 study (A4250-003) data, both low and high dose groups are assumed to have the same positive treatment effects in both the serum bile acid and pruritus endpoints in the simulation. For serum bile acids, binomial distributions were used to simulate the proportion of responders to estimate the power. The simulated proportions were analyzed using the Cochran-Mantel-Haenszel (CMH) test to generate the following 1-sided p-values: both odevixibat arms pooled vs. placebo, low dose vs. placebo, and high dose vs. placebo. Assuming 60% responders in the odevixibat arms and 10% responders in the placebo arm, the power to claim significance for a particular odevixibat arm after multiplicity adjustment is approximately 94%. The probability to claim significance for at least one arm, and for both arms are approximately 99% and 91%, respectively. If the response rates are 50% in the odevixibat arms and 10% in the placebo arm, with 20 patients per arm, the probability to claim significance for a particular odevixibat arm after multiplicity adjustment is approximately 82%. The probability to claim significance for at least one arm, and for both arms is approximately 91% and 73%, respectively.

For the proportion of positive pruritus assessments at the subject level in pruritus scores, beta-binomial distributions were used for power simulations since the binary results of the individual assessments within a subject are likely correlated [9]. The effect size was 1.0526 from the original sample size calculation using change from baseline as the endpoint. The same effect size was assumed for the current endpoint for the low and high dose vs. the control. A difference of 15%, 20%, 25%, and 30% in proportion of positive pruritus assessments were considered in power simulation. Within each difference, proportions of positive assessments in the placebo arm ranging from 15% to 35% were considered. Subsequently, the proportion of positive

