## 8.9 Blinded analysis

### 8.9.1 Pruritus Responder Definitions

Blinded analyses of Albireo ObsRO and PRO eDiary data were to be performed after 50% or more of the planned patients have completed the Week 24 Treatment Period. The actual number of 24-week treatment completers included in the analyses was 45 (~73%). The blinded analyses were used to estimate a threshold of clinically meaningful change (i.e., the responder definition) in Albireo ObsRO and PRO pruritus scores. Please refer to the psychometric analysis ([Pruritus Evidence Dossier](#)) for details. The analyses were performed by a group [REDACTED], independent from both the study team and the sponsor.

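### The supportive multiple imputation for pruritus fits each month's model to placebo completers alone: a small loss with 16 to 18 donors, but an unstable analysis with only 10 to 13

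*SAP*

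**What the plan says.** SAP 8.6.3.1 (US primary endpoint) adds a supportive MMRM on monthly averages of change from baseline, six for AM and six for PM, compared in the last 28 days. Because data may be missing not at random, a "missing monthly average will be imputed with data from control arm completers using multiple imputation (MI").

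- **Step 1** fills intermittent gaps by MCMC and creates 200 data sets.
- **Step 2** defines the donors, subgroup a: "Completers in the control arm without a missing average at the last 4 weeks". They are used to impute anyone in any arm who lacks that last average.
- **Step 3** imputes the remaining monotone gaps chronologically in Proc MI. No predictors are listed.
- **Exception:** active patients who leave for reasons such as relocation may be imputed from active completers.

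A tipping-point analysis follows only if this analysis is significant. The same procedure is repeated for AM and PM scores and for the daily worst score.

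Two other places bear on the number of donors. Section 3.1 describes an exit route into the open-label extension that was open until the sixth amendment came in: "patients who had completed at least 12 weeks of the Treatment Period and had either no improvement or intolerable symptoms were eligible". Section 8.9.1 says of the blinded psychometric analysis: "The actual number of 24-week treatment completers included in the analyses was 45 (~73" per cent).

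**The concern.** A regression that uses the whole month history, fitted in part of one arm of about 20, can run short of residual degrees of freedom. The imputed values, and hence the treatment contrast, then carry noise from the donor model that has nothing to do with the drug. If that noise makes the result non-significant, the tipping-point analysis is not run.

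The Week 12 exit route makes few placebo donors plausible. Exit for lack of improvement would be expected to thin placebo more than the active arms, just before months 4 to 6.

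Elsewhere the SAP does plan for sparse data: CMH strata are pooled (8.6.1.1), age categories may be pooled if the logistic model fails to converge (8.6.3.1), and analyses are withheld below 10 patients for child-reported PedsQL (8.6.5) and for subgroups (8.8). This imputation has no such rule.

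A second issue is selection. A placebo patient observed in month 4 who then leaves is excluded from the month-4 model, although that patient's month-4 score is known. If patients leave because they score badly, the remaining donors look better than the arm did.

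**Working it through.** **Inputs from the SAP.** Section 5: "simulations with 5,000 iterations using 20 patients per arm were conducted to estimate the power after multiplicity adjustment". Section 3.1: patients "will be randomized on Day 0 (Visit 3) in a 1:1:1 fashion". Section 5: the aim is to "control the 1-sided overall type I error rate for the two odevixibat treatment comparisons vs. placebo at the 0.025 level". Section 5: "The effect size was 1.0526 from the original sample size calculation using change from baseline as the endpoint".

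**The plan's own figure.** For one unadjusted comparison, the normal approximation gives Φ(1.0526 × √(20/2) − 1.96) = Φ(3.329 − 1.960) = 91.4%. Simulating the closed test gives, for a particular arm / at least one / both:

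- normal data: 89.9 / 95.8 / 83.8%
- beta-binomial data, 336 assessments: 88.2-89.3 / 93.7-95.3 / 81.8-83.1%

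The SAP states about 89 / 95 / 83%, so its power is reproduced.

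**How many donors?** The SAP does not say. From Section 8.9.1, 45/0.73 = 61.6, so about 62 patients and at most 62 − 45 = 17 non-completers. Spread evenly, 45/3 = 15 placebo completers. Patients still on treatment at that cut would not be counted, so this is a floor on completion, and it is not given by arm. Twelve donors out of 20 needs 40% placebo non-completion, which is an assumption.

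**Residual degrees of freedom.** Assume month 6 is regressed on an intercept, baseline and five earlier months: 7 coefficients, so df = donors − 7. The drawn residual variance is inflated on average by df/(df − 2).

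| Placebo donors | df | Variance inflation | One-dose power, correlation 0.7 |
|---|---|---|---|
| 18 | 11 | 1.22 | 89% |
| 16 | 9 | 1.29 | 86% |
| 15 | 8 | 1.33 | 82-85% |
| 14 | 7 | 1.40 | 79% |
| 12 | 5 | 1.67 | 65-70% |
| 10 | 3 | 3.00 | 39% |

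Complete data give 91-93%. The power column comes from simulation with 20 per arm, effect 1.0526 SD, monotone exit after months 3 to 5, 100 imputations, 700 to 1,000 trials per scenario, Rubin's rules, and a month-6 ANCOVA standing in for the MMRM. The exit numbers and the correlations (0.5 to 0.85 between months, −0.3 with baseline) are assumptions.

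With 12 donors and 3 dropouts per active arm, power runs from 53% (correlation 0.5) to 80% (0.85). The median SE is 0.42, against 0.30 with complete data. If PFIC type and age category also enter, there are 7 + 1 + 2 = 10 coefficients. Power at 12 donors is then about 18-25%, and at 10 donors the fit fails in two thirds of trials.

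**Effect of a pooled model.** The regression is fitted to all arms with a treatment term and common slopes, and values are imputed at the placebo level:

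| Placebo donors / dropouts per active arm | Correlation 0.5 | 0.7 | 0.85 |
|---|---|---|---|
| 12 / 3 | 53 → 84% | 68 → 88% | 80 → 90% |
| 15 / 5 | 71 → 87% | 82 → 90% | 88 → 92% |

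With 18 donors and 2 active dropouts per arm the gain is 1 to 3 points.

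A second simulation, with non-improvers leaving after months 3 to 5, gave 81 → 85% at about 16 donors, 51-63 → 69-77% at about 13, and 17-25 → 55-71% at about 10.

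**Effect of using all placebo patients observed through each month.** Power barely moves: 68.1% with completers against 68.9% at 12 completers and correlation 0.7, and at most about 5 points in any scenario. The month-6 regression can only use patients with month 6 observed, so its donors do not change. The bias does change. With completers only, imputed placebo month-6 values shift by −0.08 SD at 35% placebo exit and −0.23 SD at 56%. Under other assumptions (SD 0.8, 30-60% exit) the shift is −0.01 to −0.12 points. With all observed placebo patients it is about zero.

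**The case against.** The strongest reply is that this is a supportive analysis, that estimating the reference model in the control arm is a legitimate form of control-based imputation, and that nothing shows donors will be scarce. Much of that stands. Several stronger readings are tempting and should be set aside.

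- **A reader might infer from the 73% that about a dozen placebo patients completed.** The figure is a floor on overall completion at a blinded data cut. Even taken as final and spread evenly, it leaves about 15. The Week 12 exit applied only before amendment 6, and no count is given.
- **A reader might infer that the SAP specifies a seven-coefficient regression.** It lists no predictors; seven is what results if every earlier month and baseline are used.
- **A reader might blame the restriction to completers for the lost power.** That restriction causes the selection bias. The lost power comes from fitting a long history in one small arm.
- **A reader might take this as the only protection against informative missingness.** The primary analysis already counts missing assessments as negative, and a second denominator rule is also analysed. This is the only multiple imputation for pruritus, and only its own tipping point depends on it.

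The selection bias also has no established net direction for the treatment contrast. It flatters imputed placebo dropouts, which works against the drug, and imputed active dropouts, which works for it. The relocation exception adds donors only for some active patients and is optional.

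**Conclusion.** The point holds conditionally. With 16 to 18 placebo completers the planned imputation costs about 2 to 12 points of one-dose power (2 to 8 at correlation 0.7). With 10 to 13, and each month regressed on all earlier months, it becomes unstable and loses roughly 12 points (12 donors, correlation 0.85) to 50 or more (10 donors: 91-93% down to 39%). The number of donors, the predictors and the correlations are assumptions; the Week 12 exit route makes the lower range plausible but does not establish it.

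The bias towards improvement does not depend on small samples. It arises whenever exit follows poor scores, and it grows with placebo exit. A reader might extend the problem to the trial's stated power or its primary result; neither follows, because the stated power is reproduced and the primary pruritus analysis does not use this imputation.

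**What to change.** Amend steps 2 and 3 of 8.6.3.1 before unblinding.

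1. For each month, use all placebo patients observed through that month as donors. This removes the selection bias and needs no extra assumption, but adds little power.
2. To recover precision, fit each month's regression to all arms with a treatment term and common slopes on earlier months, and impute at the placebo level. The cost is an assumption of common slopes across arms. For baseline this is stronger than the planned MMRM, which has a treatment-by-baseline interaction; that term can be kept in the imputation model.
3. List the predictors, and state a minimum number of donors with a fallback.

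The 200 imputations, the MMRM and the tipping-point analysis can stay as they are. The work is SAP wording and a few lines of code.

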## 7 STATISTICAL CONSIDERATIONS AND ANALYSIS

### 7.1 Handling of missing data and/or invalid data and outliers

#### 7.1.1 Handling of Missing data for efficacy endpoints

##### 7.1.1.1 Pruritus Endpoint

In the primary analysis of the pruritus endpoint, all intermittently missing assessments will be classified as negative pruritus assessments (that is, not meeting the definition of a positive assessment as defined in Section 4.1). Similarly, all missing planned assessments after premature treatment discontinuation will be counted as negative pruritus assessments. All planned assessments after death or initiation of rescue treatments such as biliary diversion surgery or liver transplantation will be counted as negative pruritus assessments. Both on-treatment and off-treatment pruritus assessments up to Day 168 will be included for analysis.

In general, all 336 (=168 x 2) assessments planned over the 24-week treatment period will be included in the denominator of the endpoint definition. However, if the last pruritus assessment for a patient who completes treatment (i.e., completes Week 24 assessment) is reported prior to Day 168, then the denominator used for analysis will be (the last report day x 2). The last report day will be determined for ObsRO and PRO instruments separately.

For the analysis of the pruritus endpoint, an additional method will also be used to calculate the proportion of positive pruritus assessments up to the last report day before or on Day 168. In other words, the denominator to calculate the proportion will be (the last report day x 2). All missing data before or on the last report day will be considered as negative assessments.

In addition, a multiple imputation method will be performed for pruritus assessments as a continuous endpoint by considering the impact of intermittently missing data as well as intercurrent events (Protocol Section 11.2.2.2). Moreover, a tipping point analysis will be performed to further evaluate the influence of missing data. The details of this are addressed in the Section 8.6.3.1.

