
Baseline for proportion of patients experiencing at least a 70% reduction in fasting s-BA and for s-BA change from baseline
	
Fasting s-BA baseline will be calculated as the average of the last 2 values prior to the first dose (see also Appendix B). If only one non-missing value is available, it will be used as baseline.

End value for proportion of patients experiencing at least a 70% reduction in fasting s-BA and for s-BA change from baseline
	
The end value is the average of the values at Weeks 22 and 24 after the start of double-blind treatment. (Appendix B). If one value is missing, then the non-missing value will be used as the end value. If both values are missing, then the end value is missing.

Baseline, daily, weekly and monthly score by AM and PM respectively (scratching, itch severity)
	
For both the Albireo ObsRO scratching item and the Albireo PRO itch severity score:
 
All non-missing AM scores from the period of 14 days prior to or on the first dose day of study medications will be averaged as baseline.
 
All non-missing PM scores from the period of 14 days prior to the first dose day of study medications will be averaged as baseline.
 
Baseline score will be considered missing if <math>\geq 8</math> out of 14 assessments in the 14 days are missing (i.e. 50% rule is applied based on the number of planned assessments).
 
A weekly AM (PM) score will be calculated by averaging all non-missing AM (PM) scores in a week. A weekly score will be considered missing if <math>\geq 4</math> out of 7 AM (PM) scores in a week are missing.
 
A bi-weekly AM (PM) score will be calculated by averaging all non-missing AM (PM) scores in 2 weeks. A bi-weekly score will be considered missing if <math>\geq 8</math> out of 14 AM (PM) scores in 2 weeks are missing.
 
A monthly AM (PM) score will be calculated by averaging all non-missing AM (PM) scores in a month (28 days). A monthly score will be considered missing if <math>\geq 15</math> out of 28 AM (PM) scores a week are missing.

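### The three imputation subgroups in the supportive pruritus MMRM leave no place for a non-completer who has a last-4-week average

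*SAP*

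**What the plan says.** Section 8.6.3.1, under the US primary endpoint, plans a supportive analysis of pruritus as a continuous outcome. Monthly (28-day) averages of change from baseline are formed for AM and PM. Missing averages are imputed from control-arm completers, and an MMRM compares treatments over the last 28 days. Step 1 creates 200 data sets. Step 2 then classifies patients as:

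- (a) "Completers in the control arm without a missing average at the last 4 weeks"
- (b) anyone, whichever the arm, for whom that average is absent
- (c) "Completers in the active arm without a missing average in the last 4 weeks"

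Patients in (a) supply the imputations for (b). Step 4 reads: "After the imputation, all subjects in the 3 subgroups are pooled and the data are sorted by the imputation ID from step 1". Step 5 fits the MMRM to the result. If that is significant, a tipping-point analysis shifts the imputed scores in steps of 0.1.

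Three other parts of the SAP matter here:

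- Section 7.1.1.1 ties completion to treatment and the final visit, not to the diary. It speaks of "a patient who completes treatment (i.e., completes Week 24 assessment").
- Appendix A sets the rule for a monthly AM or PM score: it is missing when 15 or more "out of 28 AM (PM) scores a week are missing" (the 28-day month is evidently meant). Fourteen observed scores are therefore enough.
- Section 6.1 makes the FAS, all randomized patients with at least one dose, the primary efficacy set.

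**The concern.** Subgroups (a) and (c) each impose two conditions: the patient is a completer, and the last-4-week average is present. Subgroup (b) imposes one: the average is absent. A non-completer whose average is present meets neither definition. Since "After the imputation, all subjects in the 3 subgroups are pooled" is the only description of what goes forward to the MMRM, a programmer who follows the steps as written loses that patient entirely, with all monthly averages and not only the last, in every imputed data set.

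The loss would depend on an event after randomisation (stopping treatment), and it would occur in an analysis whose stated purpose is to take account of missing data and intercurrent events. Observed outcomes of late discontinuers would be discarded while early discontinuers were retained through imputation. The tipping-point analysis uses the same pooled data and would inherit the omission.

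**Working it through.** The SAP attaches no figure to this step. The simulated pruritus power in Section 5 (about 89%, 95% and 83% for a particular arm, at least one arm and both arms) reproduces at 88.6–89.1%, 94.5–95.1% and 82.7–83.4%. It concerns the proportion endpoint and does not depend on the subgroups.

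**Step 1: are the subgroups exhaustive?** Cross arm, completion of treatment, and presence of the last-4-week average:

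| Arm | Completer | Last-4-week average | Subgroup |
|---|---|---|---|
| Placebo | yes | present | a |
| Placebo | yes | missing | b |
| Placebo | no | present | none |
| Placebo | no | missing | b |
| Active | yes | present | c |
| Active | yes | missing | b |
| Active | no | present | none |
| Active | no | missing | b |

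Six of the eight cells are assigned. The two left over are the non-completers with an observed average.

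**Step 2: can such a patient exist?** Appendix B runs the Week 24 diary window from the Day 141 PM entry to the Day 169 AM entry. That gives AM entries on Days 142–169 and PM entries on Days 141–168, 28 of each. Suppose drug and diary both stop after Day d, with no earlier gaps:

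- AM scores observed = d − 141
- PM scores observed = d − 140

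An AM or PM average is missing if 15 or more of 28 scores are missing. For AM and PM combined, Appendix A sets the cut at 29 or more of 56.

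| Last diary day | AM observed / missing | PM observed / missing | Combined observed / missing |
|---|---|---|---|
| 154 | 13 / 15 (average missing) | 14 / 14 (present) | 27 / 29 (missing) |
| 155 | 14 / 14 (present) | 15 / 13 (present) | 29 / 27 (present) |
| 158 | 17 / 11 (present) | 18 / 10 (present) | 35 / 21 (present) |
| 161 | 20 / 8 (present) | 21 / 7 (present) | 41 / 15 (present) |

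From Day 155 all three averages count as observed. No off-treatment entry is needed for this.

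**Step 3: is that patient a non-completer?** Section 3.3 has an early withdrawal undergo the end-of-treatment assessments at that time. In Appendix B, Table 3.1, a visit on Days 141–161 maps to Week 22, and Week 24 begins on Day 162. A patient who stops and has the exit visit between Day 155 and Day 161 therefore has no assessment in the Week 24 window, yet has a valid last-4-week average. Steps 1 and 2 place that patient in no subgroup.

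**Step 4: scale.** At the planned 20 per arm, each such patient is 1/20 = 5% of an arm. The document does not say how many there are.

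**The case against.** The best defence is that step 2 assigns imputation roles and does not define an analysis population: (a) are donors, (b) are recipients, (c) are neither. The SAP says that it simplifies the description to imputation from placebo completers. No sentence excludes anyone, whereas elsewhere the SAP states exclusions outright (the baseline-score analysis in Section 8.6.3.1, the responder analysis in Section 8.6.4). With the FAS as the default efficacy set, a patient with nothing to impute would naturally enter the MMRM as observed. This is plausible and may be what was meant. It is not what step 4 says, and the result should not depend on a programmer's guess.

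A second defence is that the group is narrow. This stands. Patients who left well before Day 154, including those who moved early to the extension study, would mostly lack the average and fall in (b). Someone who stopped at Day 158 but attended on Day 162 or later has a visit in the Week 24 window, and the SAP does not settle whether that makes the patient a completer.

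A reader might infer a wider group from the rule that "Both on-treatment and off-treatment pruritus assessments up to Day 168 will be included for analysis". With 28 days of complete diary after the last dose, last doses from about Day 127 (AM) or Day 126 (PM) would qualify. That rule, however, is written for the primary proportion endpoint, in Section 7.1.1.1 and again in Appendix A. For the continuous analysis, Section 7.1.1.1 refers intercurrent events to a protocol section not shown here. If scores after discontinuation are set to missing there, only the late stoppers above remain.

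**Conclusion.** The subgroups in step 2 are not exhaustive, and step 4 read literally drops observed data from non-completers who have a last-4-week average. This holds without off-treatment data, given a diary complete up to about Day 155–161 and no Week 24 assessment.

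The effect is confined to the supportive MMRM with multiple imputation and its tipping-point analysis. The primary ANCOVA, the rank-based ANCOVA and the last-report-day analysis do not use these subgroups, so any inference that the primary FAS comparison is compromised is not supported.

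The number of patients affected cannot be computed from the document and is probably small, possibly zero. A reader might also try to size the bias against the 0.1 tipping-point step. The SAP gives neither the number of such patients nor how their outcomes differ. The step moves only imputed scores, so it is not on the same footing as a shift in a whole-arm mean. No bias figure is justified.

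**What to change.** Keep (a) as it stands, so that donors remain control-arm completers as Section 8.6.3.1 intends. Add to step 2 a subgroup (d): non-completers in any arm with a non-missing last-4-week average, analysed as observed and not used as donors. Change step 4 to pool all FAS patients.

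Defining (a) by an observed average alone would also close the gap, but it would admit placebo non-completers as donors, against the stated imputation rule, and is not advised.

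The cost is one sentence of SAP text and minor programming, with no new data and no change to sample size or power.
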